in Toronto. Advertisements, flyers, and in person recruitment will be employed to collect the necessary sample size for the study. The recruitment procedures will run in line with the approved guidelines from the UHN research ethics boards. Participants will not be coerced into participating and will be informed that they have the right to withdraw at any time during the experimental procedures. They will also be informed they have the right to withdraw their data prior to publication. Participants will be briefed and consented on recruitment prior to commencing the study procedures. Participant treatment allocation will be recorded on a separate document until all of the data collection is complete and the data is analyzed.

Eligibility Criteria

Female or male participants who meet the following inclusion criteria will be included in the study: (1) participants are healthy with no past medical history (2) a visual analogue score below 3 indicating low pain severity, however, ideally who complain of no pain (3) right or left handed, (4) normal body mass index, (5) have sufficient command of the English language to provide informed consent and to understand the study protocols, (6) participants agree to sign a consent to volunteer for the research.

Exclusion Criteria

Participants who meet one or more of the following criteria will be excluded: (1) history of pain, (2) physical examination detection of myofascial trigger points, (3) participants present with a history of pain related disturbances such as poor sleep, cognitive disturbances, psychiatric disorders, (4) history of general medical disorder that may affect the outcome of the study such as diabetes mellitus, (5) and a history of cervical radiculopathies or (6) history of inflammatory arthropathy.

Experimental Protocol

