Capsaicin will be applied directly to the region of the innervation zone at the muscle belly to sensitize the neurons within the region of taut band development. Topical and intramuscular capsaicin will be used. The capsaicin formula will be compounded by a registered pharmacist. Topical capsaicin will be delivered in a cream and injectable capsaicin will be intermixed with saline prior to injection. The control group in the topical capsaicin arm will be treated with the cream base used during the experiment without added capsaicin and the injection arm will be injected with saline. A trained medical professional on the research team will apply the topical capsaicin or topical placebo treatments. The region of topical application will measure 5cm squared in the dermatome zone location to cover an area of approximately 25cm². A trained physician in physical medicine and rehabilitation will deliver injectable capsaicin using a 27-gauge needle at the location of the superior fascia of the upper trapezius muscle with ultrasound guidance. The fascial layer was chosen as it is the region with the lowest pressure pain threshold relative to skin and muscle, suggesting a high density of nociceptors within the layer, and it possesses connections to the spinal cord.[27] Changes in muscle fascia properties and nociception at muscle fascia, compared to nociception at muscle or subcutaneous tissue, has also been implicated in the development of pain.[28,29] Furthermore, intramuscular capsaicin will also be injected using ultrasound guidance to avoid the superior or inferior fascia.

To confirm the presence of central sensitization, brush allodynia will be used to detect mechanical hyperalgesia outside the region of primary nociception—region of topical placement or injection—which is the region of secondary hyperalgesia.[13-15] The size of the region of secondary hyperalgesia will be measured to characterize the extent of central sensitization. This will be accomplished using a tape measure and the perpendicular dimensions of the region of secondary hyperalgesia will be recorded in square centimeters.

Ultrasound analysis

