The Delsys Trigno system, which includes sensors, the Trigno base station, and the EMGworks software will be used to decompose the acquired EMG signals into individual motor units. The following parameters will be analyzed: the firing times and frequency of individual motor units, motor unit action potential amplitude and shapes[36-38], the root mean square value (RMS) of each channel and of the entire signal[16], the coefficient of variation for force steadiness[39], and the centroid of the EMG signal in the cranial-caudal and the medial-lateral directions[16]. This will be repeated for each contraction.

Intramuscular EMG analysis

A 27g monopolar electromyography needle will be placed into the midbelly of the upper fibers of the trapezius muscle using ultrasound guidance. The intramuscular EMG signals will be measured using Cadwell Sierra Wave. Since this system does not offer motor unit decomposition, we will use the intramuscular EMG analysis to provide us with more details of the gross EMG measurements such as the overall RMS value, the coefficient of variation for force steadiness, and the centroid measurements.

Determination of Central Sensitization:

Before measuring outcomes, approximately 20 minutes after capsaicin application we will analyze the area of secondary hyperalgesia for each study subject, then determine whether central sensitization has in fact been induced. The presence of central sensitization is confirmed by expansion of the receptive field and area of secondary hyperalgesia beyond the 25 cm² initial application area. If it has, the study participant will undergo the rest of the experimental methodology. If it has not, the capsaicin will be applied once more and the region of secondary hyperalgesia will be remeasured in 20 minutes later. The above described process for confirming the presence of central sensitization will take place again. If the study participant has not had sensitization at this stage they will be withdrawn from the study.

Primary Outcomes

The primary outcome measures:

1. Textural regional changes
2. Recruitment and Amplitude regional changes

These will be recorded for each arm of the study, please see figure 1.

Secondary outcomes:

1. A record of adverse events

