2. Safety evaluation The investigating physician monitors the patient clinically for signs of distress. The methods and timing for assessing, recording, and analyzing safety parameters. Any signs of distress noted by investigating physician will be assessed clinically and appropriately managed. The information will be recorded on the patient's data form. The study team will discuss all incidents and any potential causal link to the study interventions. Patients will be provided with a contact number for the principal

investigator in order to report any changes that occur during or after the study. Our publication will include a list of any adverse events or intercurrent illness encountered. Any patient who experiences an adverse event will be triaged to their family physician or local emergency department as necessary. They will be contacted after to obtain information on the course of their treatment and the outcome of the event.

3. Sample size calculation.

Using GPower V3.0.10 (Dusseldorf, Germany), considering a medium effect size (Hedge's G) of 0.5 and a moderate correlation coefficients (0.5) among repeated measures, sample size calculation determined that a minimum of 70 participants would be required to detect differences via repeated measures ANOVA (two measurement as before and after among 7 groups) with 80% power and an alpha of 0.05. We aim to recruit 84 participants to account for potential attrition (~20%) of participants given the study duration and frequency of follow-up visits.

We plan to recruit equal number of men and women. To date, there are no reported sex differences in induction of Central Sensitization using Capsaicin among males and females with neurological impairments.

4. Statistical analysis plan

Baseline participants' characteristics including demographics will be analyzed using appropriate descriptive statistics. Mean and standard deviation will be calculated for continuous variables. Categorical variables will be presented as numbers and percentages. To test the change in ultrasound images from baseline to experimental conditions, the

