texture features will be computed in MATLAB and principal component analysis will be computed to reduce the variables. A repeated measures MANOVA will be applied for each intervention group. To test the change in EMG within and between groups a repeated measurement ANOVA will be applied considering each intervention group as a factor. The dependent variable would be considered as pain intensity, duration, and area of pain in separate analysis. Data distributions would be first checked with the Shapiro-Wilk to conform the normal distribution of the data. Additionally, we will test for the homogeneity of variance using Mauchly's test as well as correcting the degrees of freedom if necessary [40]. If the assumption of normality not met, for all skewed data an appropriate transformation will be used. We will construct univariate and multivariable linear regression models of differences in EMG amplitude (differences between after and before) as a function of intervention groups when adjusted for important covariates. Due to small sample size in each group, there is not possible to adjust for several covariates. Therefore, in a univariate model we will find the most important ones. For initial selection of relevant variables, all variables with a p-value ≤ 0.2 in the univariate analysis will be selected and retained in the multivariable analysis.

All Statistical analyses will be conducted with SAS for Windows (version 9.3; SAS Institute, Inc, Cary, NC). Using a two-sided test a P-value ≤ 0.05 will be considered as statistically significant.

Discussion

This will be the first study that assesses the effect of capsaicin induced central sensitization on ultrasound texture features and muscle motor unit activity. Findings from this

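### If area of pain means the screened area of secondary hyperalgesia, its before-after test in retained participants is near-certain to be significant and says little about capsaicin dose

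*Combined protocol and SAP*

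**What the plan says.** Section 4 (Statistical analysis plan) gives the model: "To test the change in EMG within and between groups a repeated measurement ANOVA will be applied considering each intervention group as a factor". The next sentence names the variables: "The dependent variable would be considered as pain intensity, duration, and area of pain in separate analysis". Section 3 (Sample size calculation) describes the layout of that ANOVA as "two measurement as before and after among 7 groups".

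The protocol does not define *area of pain*. The one area it describes measuring is in the section on inducing central sensitization, where "the perpendicular dimensions of the region of secondary hyperalgesia will be recorded in square centimeters". Under Determination of Central Sensitization, "approximately 20 minutes after capsaicin application we will analyze the area of secondary hyperalgesia for each study subject", ahead of the outcome measurements. Sensitization counts as present if there is expansion of the "area of secondary hyperalgesia beyond the 25 cm² initial application area". A participant who falls short has one repeat application and a second reading. After that: "If the study participant has not had sensitization at this stage they will be withdrawn from the study".

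The baseline measurements that are named are EMG and ultrasound images. No baseline area is described. Eligibility accepts a visual analogue score below 3, "however, ideally who complain of no pain", and a history of pain is an exclusion.

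**The concern.** The quantity that decides who stays appears to be tested again as a response. If it is the same area, every analysed after-value exceeds 25 cm², and it is set against a before-value that is not recorded and is probably close to zero. A significant time effect would then follow from the baseline and the retention rule together, at either dose and in any group made up of retained participants. The retention rule is written for each subject, so read literally it covers the cream-base and saline controls too.

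At stake is interpretation. A significant change in area in every retained group could be read as evidence that capsaicin worked, or as support for a dose-response argument. The between-group comparison would also be made only in people selected on how they responded after randomisation, some of them after two applications.

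**Working it through.** **The plan's own figure.** No figure is given for area of pain. The only number attached to this ANOVA is the minimum of 70 participants. Taking the stated effect of 0.5 as f = 0.25 (an assumption), with correlation 0.5, two measurements and 7 groups, the interaction test has λ = f²·N·m/(1−ρ). At N = 70 this is 0.0625 × 70 × 2 / 0.5 = 17.5, which gives 86.6% power. The smallest N for 80% power is 62 (63 in equal groups), so 70 is not reproduced. That is a separate matter; here the sample size serves only to set group sizes: 70/7 = 10, 84/7 = 12, and 84/6 = 14 if the six groups of the Study Design section are used.

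**Assumptions for the check.** Area of pain is the screened area; before = 0; the spread of areas is unknown, so a range is used.

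**When can the within-group test miss?** With before = 0, t = mean/(SD/√n). It fails to reach P ≤ 0.05 only if SD/mean exceeds √n / t(0.975, n−1):

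- n = 10: √10 / 2.262 = 1.40
- n = 12: √12 / 2.201 = 1.57

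With a floor of 25 cm², that needs extreme skew. For n = 10, take nine values at 25 and one at 223. The mean is 44.8, the SD is (223 − 25)/√10 = 62.6, and t = 44.8/(62.6/√10) = 2.26, just at the boundary.

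**Simulated rejection of the within-group test, before = 0:**

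| Model for retained areas | n per group | Rejection |
|---|---|---|
| 25 cm² plus lognormal excess, mean 10, CV 0.3–1.5 | 8, 10, 14 | 99.6–100% |
| Lognormal truncated above 25, medians 10–60, log-SD 0.4–0.7 | 10, 12 | 99.6–100% |
| Same, log-SD 1.0 | 10, 12 | 94–99.6% |

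The pooled time effect at N = 70 (log-SD 0.7) was significant in every run. A non-zero baseline changes little: with an assumed exponential baseline (mean 5 cm², capped at 20), rejection was 99.2–100% at log-SD 0.4–0.7 and 93–99.6% at 1.0. The plan says skewed data will be transformed; with log(1+x), rejection was 100% in every setting run. A sign test on ten positive differences gives P = 2 × 0.5¹⁰ = 0.002.

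**How much is due to the retention rule?** Removing the 25 cm² floor from the first model leaves rejection at 75–100%. At n = 10 it is 100%, 99.95%, 96.7% and 85.1% for CV 0.3, 0.6, 1.0 and 1.5. So the near-zero baseline forces much of the result when everyone has some area. The rule matters far more when many have none: with half the participants at zero (n = 10, CV 1.0) the test without the rule rejects in 44% of runs.

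**Between groups.** When groups do not differ, the group-by-time test rejects in about 4% of runs, so it is not forced. For assumed medians of 40 and 60 cm² (log-SD 0.7, n = 10 each), power is about 18–19% without the filter and 13–14% with it.

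**The case against.** The strongest objection is that the variable is inferred. The protocol never equates area of pain with the area of secondary hyperalgesia, and it takes the screening reading before the outcomes, which could mean the two are distinct. That stands, and the point is therefore conditional. But if another area is meant, the plan does not say how or when it is measured, so the SAP needs correcting either way.

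A reader might infer stronger things that the documents do not support:

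- *Baseline is zero by definition.* It is not stated. A score below 3 is allowed, and absence of pain is only the ideal. Near zero is plausible because a history of pain is excluded.
- *The test cannot fail.* It can, with very skewed areas in small groups.
- *The retention rule alone creates the result.* The figures without the floor show that it does not.
- *The type I error is inflated above 5%.* A participant who goes from no area to more than 25 cm² has truly changed. The fault is that the test is uninformative and selected, not that it gives a false positive.
- *Dose differences are hidden.* The loss of power is modest, and power was low to begin with.

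It is also fair that area of pain is not a listed primary or secondary outcome, that none of research questions a to f concerns it, and that the protocol already uses the area to confirm and characterise sensitization. This limits the consequence.

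**Conclusion.** The point holds conditionally. If area of pain is the screened area of secondary hyperalgesia and its baseline is near zero, the within-group time effect among retained participants is near-certain to be significant: about 94–100% of simulated groups, with the low end reached only at extreme skew (log-SD 1.0) in groups of 10. Smaller groups that skewed would fall somewhat lower, since at n = 8 the SD/mean limit is √8 / 2.365 = 1.20. The result reflects the baseline and the retention rule together and carries almost no information about dose.

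The between-group comparison remains a real test, but in a subset chosen on a post-randomisation response, with a modest loss of dose contrast. The distributions and medians are assumptions, because the documents give no figures for area. No stated primary or secondary outcome is affected, so the consequence is modest; the correction is still worth making because the variable is named for testing at P ≤ 0.05.

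**What to change.** In section 4 (Statistical analysis plan):

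1. State that area of pain is the area of secondary hyperalgesia. If the sponsor means something else, define it and say how and when it is measured.
2. Remove the before-after test for area.
3. Analyse the first 20-minute reading, taken before the retention check is applied, in all randomised participants including those later withdrawn. Treat it as a manipulation check and compare it between control, 50 and 100 micrograms within each route, giving the difference with a confidence interval by a method that tolerates skew and zeros.
4. Do not present the area among retained participants as evidence of response.
5. Duration is not screened, but no before-value is described for it, so analyse it as a post-application value only.

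The cost is SAP wording: the protocol already plans the first reading for each subject, so the only practical need is to keep it for those who are withdrawn. The downside is one fewer nominally significant descriptive result.

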perform a gradually decreasing contraction to rest. This will be performed four times for each type of study intervention and before as well as after each intervention, namely topical control cream, topical capsaicin at 50ug and 100 ug, injection of the superior aspect of the superior fascia followed by intramuscular injection with these two concentrations of capsaicin. The placement of these latter will be verified by ultrasound guidance. The intramuscular needle will then be removed and participants will be bandaged and cared for appropriately by the expert physician performing the experiment. Following this, ultrasound pictures will be taken again from the same muscles mentioned previously. Participants will be re-examined to determine if there were any adverse effects from the experimental procedures. If any occurred, then these will be carefully managed by the medical members of the research team and recorded. Participants will be asked to remain at the lab for an additional 30 minutes to ensure they are well prior to leaving (Figure 2).

Central sensitization and measurement techniques

Inducing central sensitization

Central sensitization will be induced using capsaicin according to the established technique.[13,24,25] It induces increased pain severity at high doses relative to heat and elicits a dose dependent pain responses, allowing for more easily quantifiable measurements.[26] Capsaicin delivery induces both primary and secondary nociception suggesting that central mechanisms are involved in the nociceptive response, also termed as central sensitization.[13,14] Previous evidence has confirmed that capsaicin can sensitize nociceptive and mechanoheat receptors outside of the region of primary hyperalgesia, with speculation that it can also sensitize chemonociceptive receptors.[13] Therefore, capsaicin can effectively be used to induce central sensitization.

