The Sonosite Ultrasound machine located at the Toronto Rehabilitation Institute clinic will be used. The ultrasound probe will be placed onto the trapezius before and after the sensitization is induced and an ultrasonic image will be captured. Texture feature analysis will be performed using MATLAB and the Signal Processing Toolbox. Analyses will include first order parameters such as mean and standard deviation of the pixel level values, as well as second order parameters, which provide details on the spatial distribution of pixel values. These include co-occurrence and run-length matrices, local binary pattern and blob analysis[Quant text ref].

Measurement of motor unit activity using EMG

The Delsys Trigno surface EMG system will be used in this experiment. The system offers the benefit of having a 4-pin mini-grid that can extract individual motor unit data, without causing participants discomfort. The analysis will also be complemented by the use of intramuscular EMG, since it offers high location specificity when measuring EMG activity, while only a local region is analyzed. The intramuscular EMG data will be analyzed by a Cadwell Sierra Wave device.

The anatomical location for electrode placement, along the C7-acromion line, will be identified for each participant. Baseline EMG measurements, as well as the ultrasonic images will be taken from the upper trapezius muscle to obtain the baseline motor unit recruitment curve. The trapezius muscle was chosen for study since it is a common site for MTrPs, given the high load cervical muscles carry as well as the general increase sedentariness that perpetuates poor posture and cervical muscle strain, leading to trigger point presentation. Furthermore, the

trapezius muscle has been used frequently in previously published work, which analyze motor unit parameters, power spectrum and amplitude measurements.[31,32,33]

sEMG Analysis

After the identification for electrode placement and the captured baseline ultrasonic images, the area will be cleaned with alcohol and water. The Delsys Galelio sensor will be placed directly on the identified area. The EMG sensor (bandwidth of 20-450Hz) consists of 4 metal contacts for detecting the signal at the skin surface. Both the right and left sides of the trapezius will be measured.

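### Neither between-group EMG amplitude analysis guarantees adjustment for the baseline amplitude already collected; the cost is precision, not bias

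*Combined protocol and SAP*

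**What the plan says.** Amplitude change is part of the second item under Primary Outcomes. The before values exist: under Measurement of motor unit activity using EMG, "Baseline EMG measurements, as well as the ultrasonic images will be taken from the upper trapezius muscle", and under Experimental Protocol the contraction task is repeated: "This will be performed four times for each type of study intervention and before as well as after each intervention".

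Section 4, Statistical analysis plan, then gives two between-group routes.

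- **ANOVA.** "To test the change in EMG within and between groups a repeated measurement ANOVA will be applied considering each intervention group as a factor". No covariate is mentioned. The next sentence reads "The dependent variable would be considered as pain intensity, duration, and area of pain in separate analysis", so it is not certain that EMG is the outcome of this model.
- **Regression.** The plan will build "linear regression models of differences in EMG amplitude (differences between after and before) as a function of intervention groups when adjusted for important covariates". It warns: "Due to small sample size in each group, there is not possible to adjust for several covariates". Variables reaching p ≤ 0.2 "in the univariate analysis will be selected and retained in the multivariable analysis".

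Baseline EMG is not named as a covariate, as a candidate for the screen, or as a term that stays in regardless. Neither analysis is called the main one.

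**The concern.** With about 10 participants per group, efficiency matters, and the before value is usually the most useful covariate for an after value. A before-after ANOVA appears to use it, but it enters only as one of the two repeated levels. The group-by-time test therefore compares raw changes and does not adjust for where each participant started. The regression could adjust, but only if someone later puts baseline EMG on the candidate list and it then passes the screen. At stake are avoidable imprecision on a primary outcome and a covariate set that is not fixed before the data are seen.

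**Working it through.** **Inputs.** From section 3, Sample size calculation: 7 groups, two measurements, correlation 0.5, alpha 0.05, 80% power, effect 0.5, minimum 70, target 84. The SD of EMG amplitude is not given. I assume it is equal before and after, call it σ, and relax this in step 4. Correlations other than 0.5 are assumptions.

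**The plan's own figure.** For the group-by-time test with f = 0.5/2 = 0.25, λ = f²·N·2/(1−ρ) = 0.0625 × 70 × 2/0.5 = 17.5 on 6 and 63 df. Power is 86.6%, and the smallest N for 80% is 62. Entering 0.5 directly as f, with λ = f²(N−7), gives 0.25 × 63 = 15.75, power 82.1%, and a minimum of 68, or 70 in multiples of 7. Only the second reading gives 70, and it does not use the correlation. To avoid depending on this, I fix the effect at the one for which 70 participants give exactly 80% unadjusted: λ = 15.03.

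**1. Identity.** With two time points, the group-by-time F equals the one-way F on the change score. In one simulated data set of 7 × 10, both were 0.7938.

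**2. Variance.** Change score: 2(1−ρ)σ². Adjusted for baseline: (1−ρ²)σ². The ratio is (1+ρ)/2, and the SE ratio is its square root. At ρ = 0.5 the variances are 1.00 and 0.75 σ², and the SE ratio is √0.75 = 0.866.

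**3. Power and screening.** Adjusted λ = 15.03/((1+ρ)/2) on 6 and 62 df; at ρ = 0.5 this is 15.03/0.75 = 20.04. For the screen, the correlation of baseline with change is −√((1−ρ)/2). The selection probability uses Fisher's z with N = 70 and two-sided p ≤ 0.2.

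| ρ | Variance, change / adjusted (σ²) | SE reduction | Power (80% unadjusted) | N matching 70 unadjusted | Baseline selected, if a candidate |
|---|---|---|---|---|---|
| 0.5 | 1.00 / 0.75 | 13% | 91.3% | 55 | 99.9% |
| 0.7 | 0.60 / 0.51 | 8% | 86.9% | 61 | 98% |
| 0.8 | 0.40 / 0.36 | 5% | 84.6% | 64 | 92% |
| 0.9 | 0.20 / 0.19 | about 3% | 82.3% | 67 | 72% |
| 0.95 | 0.10 / 0.0975 | about 1% | 81.1% | 69 | about 51% |

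Simulation of 20,000 trials, 10 per group, gave power of 80.3 against 90.5% at ρ = 0.5, 80.3 against 86.4% at 0.7, and 79.5 against 83.8% at 0.8. The SD of a pairwise contrast fell from 0.445 to 0.390σ (12%), 0.345 to 0.320σ (7%) and 0.284 to 0.272σ (4%). The documents disagree on the number of groups, but this hardly matters: at ρ = 0.5, 6 groups give 91.2% and 9 give 91.5%.

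**4. Unequal variances.** If the after SD is c times the before SD, the variance ratio is c²(1−ρ²)/(1+c²−2ρc). For c = 0.8 the SE reduction is 24%, 21% and 20% at ρ = 0.5, 0.7 and 0.8. For c = 1.25 it is 6%, 1% and 0%.

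**The case against.** The strongest reply is that nothing here is wrong, only less efficient than it could be. The change-score comparison is valid under randomisation, the sample size was set for the same before-after test, and the trial is exploratory. All of that stands.

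The regression half is weak in practice. If baseline EMG is a candidate, it enters almost always at the plan's correlation. Where it often fails to enter (28% of the time at 0.9), there is little to gain. This also stands. What remains is that no candidate list exists, so inclusion is left to a later choice.

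The ANOVA half depends on reading EMG as its dependent variable. If the sentence naming pain variables is literal, the baseline EMG argument does not reach that model, and the regression is the only amplitude comparison left.

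The power gain is for an omnibus test at a back-solved effect. For one pairwise contrast of 0.5 SD with 10 per group at ρ = 0.5, power rises only from about 20% to 25% (normal approximation), so adjustment does not rescue the individual contrasts.

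A reader might infer more than the documents support:

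- **Bias.** Omitting baseline does not bias a randomised comparison.
- **Inflated type I error from the screen.** In 4,000 simulated null trials, screening baseline alone gave rejection rates of 4.2% at ρ = 0.5 and 5.3% at 0.8, so no inflation was shown.
- **A flat contradiction over covariates.** The plan offers the screen as its way of limiting them and calls it an initial selection. That is a tension, not a contradiction.

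**Conclusion.** The point holds as one of precision and prespecification. The plan does not guarantee baseline adjustment in either between-group analysis. If the ANOVA is an EMG analysis, its group-by-time test is unadjusted. The regression is adjusted only if baseline is a candidate and passes the screen, and then it loses nothing.

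Under equal variances the gain is worthwhile at the only correlation in the documents and fades to almost nothing as the correlation nears 1. Under the two unequal-variance cases examined, it runs from 0% to about 24% of the SE. With known parameters, adjustment is never less precise than the change score, apart from the one degree of freedom.

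Validity with or without adjustment assumes that the analysed groups remain comparable. Whether the withdrawal of participants who are not sensitised disturbs that is a separate question, and baseline adjustment would not settle it.

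**What to change.** State in section 4 that the between-group EMG amplitude comparison is a linear regression of post-intervention amplitude on randomised group, with the same amplitude measure at baseline as a fixed covariate. Using the change as outcome gives the same group contrasts once baseline is in the model. Keep baseline outside the p ≤ 0.2 screen, and name this the main between-group amplitude analysis in place of the unadjusted group-by-time test. Retain the within-group before-after estimate for research question (b), which asks about a 20 to 25% change.

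The cost is SAP wording and one residual degree of freedom (63 to 62 with 70 participants in 7 groups; 64 to 63 in 6; 61 to 60 in 9). No new data are needed. Under equal variances the minimum of 70 need not rise on this account, and one sentence in section 3 can say so. How the repeated contractions are summarised per participant, which side is analysed, which other covariates are used and how withdrawals are reported are separate points.
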